Sub-Aim 5D: Compare the 6 week postpartum depression rates of the cohort utilizing remote patient monitoring to the cohort of patients with hypertension related disorders discharged with routine care.

Hypothesis: We hypothesize that women utilizing remote patient monitoring will have lower rates of depression than women with hypertension related disorders discharged with routine care.

Sub-Aim 5E: Correlate the results of the HoneyWell Biometrics Questionnaire question number 42 to the result of the Edinburgh Depression Scale recorded at the 6 week postpartum visit. (Question number 42 is: Has your mood been more depressed this week compared to a normal week? (Rated from 1-7))

Hypothesis: We hypothesize that the HoneyWell Biometrics Questionnaire question number 42 will capture more postpartum depression than the 6 week Edinburgh Depression Scale, but that it will correlate well.

Sub-Aim 5F: Graph the blood pressure trajectory of the cohort utilizing remote patient monitoring with daily weights over 6 weeks.

Hypothesis: This is a descriptive sub-aim. We hypothesize that the postpartum blood pressure will peak at 5-7 days postpartum.

Sub-Aim 5G: Compare the 6 week postpartum blood pressure of the cohort utilizing remote patient monitoring to the cohort of patients with hypertension related disorders discharged with routine care who attended their 6 week postpartum visit.

Hypothesis: We hypothesize that women utilizing remote patient monitoring will have lower blood pressures at their 6 week postpartum visit than women with hypertension related disorders discharged with routine care.

Specific Aim 6: Conduct a follow-up satisfaction from a medical provider perspective in having their patients cared through this study, as well as the betterment of the telehealth monitoring system for future clinical use. This will be collected anonymously from providers.

Hypothesis: We hypothesize that providers of patients enrolled in this study will have had a positive experience while caring for their subject.

Specific Aim 7: Descriptive analysis of exactly what happens to women who end up with developing a hypertensive disorder in pregnancy and blood pressure trend from baseline pregnancy through 6 weeks postpartum.

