3.3. Classification/diagnosis of hypertension related disorders in pregnancy

CHRONIC HYPERTENSION	
 • SBP ≥ 140 mmHg or DBP ≥ 90 mm Hg • Pre-pregnancy or before 20 weeks
-----------------------------	--

GESTATIONAL HYPERTENSION	
 • SBP \geq140 mm Hg or DBP \geq90 mm Hg • Occurs after 20 weeks • Absence of proteinuria or systemic signs/symptoms consistent with preeclampsia
PRE-ECLAMPSIA	
 • New onset BP after 20 weeks • Two BPs SBP\geq140 or DBP \geq90 on two occasions at least 4 hours apart • AND Proteinuria with or without signs/symptoms* • OR in the absence of proteinuria new onset of any systemic finding: 
 -Thrombocytopenia (platelets <100,000K) -Renal insufficiency (serum creatinine $>$1.1 mg/dL) -Impaired liver function (\uparrowLFT 2x normal)
Eclampsia	
 • New onset grand mal seizures in woman with preeclampsia • New onset seizures 48-72 hours postpartum
Chronic Hypertension + SUPERIMPOSED PREECLAMPSIA	
 • Chronic hypertension in association with preeclampsia
PREECLAMPSIA WITH SEVERE FEATURES (one or more of the listed criteria)	
 • SBP \geq160 mm Hg or \geq110 mm Hg on at least 2 occasions at least 4 hours apart 
 -Thrombocytopenia (platelets <100,000K) -Renal insufficiency (serum creatinine $>$1.1 mg/dL) -Impaired liver function (\uparrowLFT 2x normal) 
 - Pulmonary edema - New-onset cerebral or visual disturbances 
*Proteinuria $>$5g is no longer considered for diagnosis nor is IUGR for 'severe'

3.4. Outcome variables: see attached data dictionary (Appendix I). I will plan to work with my prior IRB application request (IRB number 2016-006) using Peridata and Meriter for variables and have a prospective report built to extract patient data from for patients enrolled in this study.

4. Study procedures

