Devices and instructions will be provided by UnityPoint at Home. They will be given instructions on proper techniques for blood pressure by the labor & delivery nurses, the mobile health nurse or research coordinator if needed. It will be expected if the teaching cannot be performed by one of the nurses they will contact the research coordinator to provide this training. All individuals will have had training for proper blood pressure measurement technique prior to providing this training. The patients will be required to take the blood pressures in a seated position with their arm at heart level. Three values should be obtained and an average of these values will be used in our assessment of daily blood pressure. The patient will also be given instructions on warning signs of preeclampsia or severe hypertension and blood pressure thresholds to call the mobile health nurse or their primary obstetric clinical provider or nurse.

Once discharged from the hospital the patient will initiate their home blood pressure/weight measurements. They will be asked to take a total of three blood pressures everyday (spread out no more than five minutes apart) to validate there are not erroneous values submitted. The blood pressures and weight values will be submitted via the Honeywell device and these values will be delivered to the mobile health nurse platform. These values will need to be manually uploaded into the study database program in REDCap. The values and patient concerns will be reviewed daily by the mobile health nurse with a flowsheet algorithm that directs them when to continue with current care plan or the need to contact the physician for the patient. The patient will be contacted by a mobile health nurse on days 2 and 7 post discharge. Additionally the patient may be contacted by the mobile health nurse based on the flowsheet algorithms and patient concerns (if applicable). A telehealth note will be put into EPIC when contact with the patient is had by phone or video teleconferencing. This note will be cc'd to the primary provider for review. Daily vital signs will eventually be an automated process into EPIC, however until this is possible it will be a manual entry performed daily by the mobile nurse.

Follow Up Procedures for Patients

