APPENDIX I

Data variables to extract from EPIC Electronic Medical Records/Peridata

1. Medical record number for mother
2. Date of birth
3. Link baby to mother (Medical record number)
4. Date of birth

Demographics Maternal

5. Maternal age
6. Tobacco use
 - a. Yes
 - b. No
7. Date of first prenatal care visit
8. Body mass index at first prenatal care visit
9. Body mass index at delivery or with initial admission
10. Body mass index at second admission
11. Body mass index >30 at delivery
 - a. Yes
 - b. No
12. Maternal weight in kilograms with first prenatal care visit
13. Maternal weight in kilograms on initial admission
14. Maternal weight in kilograms within 24 hours of delivery
15. Maternal weight in kilograms within 24-48 hours of delivery
16. Maternal weight in kilograms within 48-72 hours of delivery
17. Maternal weight in kilograms within 72-96 hours of delivery
18. Maternal weight in kilograms within 24 hours of initial admission discharge
19. Maternal weight in kilograms on readmission
20. Maternal weight in kilograms on discharge from readmission
21. Maternal diabetes
 - a. Gestational
 - b. Type 1
 - c. Type 2
22. Marital status
 - a. Married
 - b. Single
 - c. Unknown
23. Insurance
 - a. Commercial
 - b. Medicaid
 - c. HMO
 - d. Uninsured
 - e. Other
 - f. Unknown
24. Race

- a. Caucasian
- b. Hispanic
- c. African American
- d. American Indian/Alaskan Native
- e. African
- f. Asian American
- g. Other
- h. Unknown

25. Ethnicity

- a. Hispanic

26. Gravidity

27. Parity (live children)

28. Gestational age rounded in weeks at delivery

29. Estimated date of delivery

30. Singleton pregnancy

- a. Yes
- b. No

31. Multiple pregnancy

- a. Twins
- b. Triplets

32. Mode of delivery

- a. Normal spontaneous vaginal delivery
- b. Operative delivery
 - i. Forceps
 - ii. Vacuum
- c. Cesarean section

33. Indication for cesarean section

- a. First stage arrest
- b. Second stage arrest
- c. Fetal intolerance of labor
- d. Fetal distress
- e. Repeat cesarean section
- f. Failed trial of labor after prior cesarean section
- g. Elective primary cesarean section
- h. Vaginal bleeding/abruption
- i. Placentation
- j. Fetal malpresentation
- k. Maternal illness
- l. Other

34. Hypertension related disorder was diagnosed in pregnancy

- a. Prior to initial admission
- b. Prior to delivery of baby (intrapartum)
- c. After delivery of baby (postpartum)
- d. Only upon readmission to hospital after initial admission discharge

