- Specific labs (report them out for each day of admission (primary and secondary) – Please give the maximum and minimum due to some individuals may have many values
 - AST
 - ALT
 - Hematocrit
 - Platelet count
 - Urine protein total in 24 hours
 - Urine protein by protein:creatinine ratio
 - Uric acid

107. Reported maternal symptoms related to hypertension

- Headache
- Visual changes
- Shortness of breath
- Chest pain
- Seizure
- Abdominal pain
- Vomiting
- Nausea

108. Total amount of Intravenous fluids given with initial admission

109. Pulmonary edema

110. Estimated blood loss volume at delivery in (cc)

111. Maternal transfusion

- Yes
- No

112. Maximum Systolic blood pressure during 1st trimester of pregnancy (top three) with date and time

113. Maximum Diastolic blood pressure during 1st trimester of pregnancy (top three) with date and time

114. Maximum Systolic blood pressure during 2nd trimester of pregnancy (top three) with date and time

115. Maximum Diastolic blood pressure during 2nd trimester of pregnancy (top three) with date and time

116. Maximum Systolic blood pressure during 3rd trimester of pregnancy (top three) with date and time

117. Maximum Diastolic blood pressure during 3rd trimester of pregnancy (top three) with date and time

118. Maximum Heart Rate during 1st trimester of pregnancy (top three) with date and time

- 119. Maximum Heart Rate during 2nd trimester of pregnancy (top three) with date and time
- 120. Maximum Heart Rate during 3rd trimester of pregnancy (top three) with date and time
- 121. Minimum Systolic blood pressure during 1st trimester of pregnancy with date and time
- 122. Minimum Diastolic blood pressure during 1st trimester of pregnancy with date and time
- 123. Minimum Systolic blood pressure during 2nd trimester of pregnancy with date and time
- 124. Minimum Diastolic blood pressure during 2nd trimester of pregnancy with date and time
- 125. Minimum Systolic blood pressure during 3rd trimester of pregnancy with date and time
- 126. Minimum Diastolic blood pressure during 3rd trimester of pregnancy with date and time
- 127. Minimum Heart Rate during 1st trimester of pregnancy with date and time
- 128. Minimum Heart Rate during 2nd trimester of pregnancy with date and time
- 129. Minimum Heart Rate during 3rd trimester of pregnancy with date and time

UPH-Meriter Telehealth Screening Test

130. self-reported response to patient's depressed mood (January - March 2019)

- a. Yes
- b. No

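### Sub-Aim 5D compares 6-week depression rates between non-randomised cohorts without collecting depression history, so imbalance in prior depression cannot be checked or adjusted for

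*Combined protocol and SAP*

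**What the plan says.** Section 2 (Objectives) gives Sub-Aim 5D as "Compare the 6 week postpartum depression rates of the cohort utilizing remote patient monitoring to the cohort of patients with hypertension related disorders", the second cohort having gone home with routine care. The hypothesis is directional: "We hypothesize that women utilizing remote patient monitoring will have lower rates of depression than women with hypertension related disorders discharged with routine care".

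The companion aim, Sub-Aim 5E, is to "Correlate the results of the HoneyWell Biometrics Questionnaire question number 42 to the result of the Edinburgh Depression Scale" at the 6-week visit. The question is given as "Has your mood been more depressed this week compared to a normal week? (Rated from 1-7").

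On the data, Section 3.4 reads "Outcome variables: see attached data dictionary (Appendix I"). That appendix is headed "Data variables to extract from EPIC Electronic Medical Records/Peridata". Its item 54 holds the 6-week Edinburgh result as a 0-30 score and as positive (10 or more) or negative.

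On the comparison:

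- Under Section 4.2, women enter monitoring by agreeing when approached, through their provider, or by contacting the coordinator themselves.
- Section 7.1 matches controls 1:1 within the same month and names no other matching factor. It describes Aims 2-5 as exploratory and unpowered, intended to inform later studies.
- Section 7.2 plans a baseline comparison of the groups, t-tests for continuous variables and ANOVA for categorical ones. It names no adjusted model.

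**The concern.** A woman who was depressed or on an antidepressant before delivery can be expected to screen positive at 6 weeks more often than one who was not. Month matching does nothing to balance that history, and willingness to take on six weeks of daily measurements may well be related to it. If the cohorts differ, the difference goes straight into the 5D comparison. Because the history is not recorded, the planned baseline comparison would not reveal the imbalance, and no later analysis of the listed data could remove it. A difference found in 5D, or its absence, could then be carried into the planning of a future trial as if it reflected monitoring.

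**Working it through.** **1. Is prior depression anywhere in the listed data?** I went through Appendix I, items 1-131.

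| Items | Content | Prior depression? |
|---|---|---|
| 5-35 | Maternal demographics, obstetric and hypertension history | No |
| 54 | Edinburgh score at the 6-week visit | No, this is the outcome |
| 82-86 | Medication lists, each limited to blood pressure drugs | No |
| 107 | Symptoms related to hypertension | No |
| 130 | Yes/No mood answer, "depressed mood (January - March 2019") | No; later clinical programme |
| 131 | PHQ-9 score, April 2019 to January 2020 | No; later clinical programme |

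No item gives a depression diagnosis, an antenatal depression score or antidepressant use. The 5D outcome is present; what is missing is a confounder. The text between Section 11 and Section 13.1 was not available to me, but Section 3.4 places the outcome variables in Appendix I.

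**2. How large could the distortion be?** The documents give no depression rate, effect size or power for 5D, so there is no figure of the plan's own to reproduce. Every rate below is an assumption.

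- r1, positive-screen rate with prior depression: 30% to 40%.
- r0, positive-screen rate without it: 8%.
- pM and pC, prevalence of prior depression in monitored women and controls: differing by 0 to 15 points.
- True effect of monitoring: none.

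The expected rate in a group is p x r1 + (1 - p) x r0, so the spurious difference is (pM - pC) x (r1 - r0).

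| Imbalance | r1 = 30% (gap 0.22) | r1 = 40% (gap 0.32) |
|---|---|---|
| 0 points | 0 | 0 |
| 5 points | 0.05 x 0.22 = 1.1 points | 0.05 x 0.32 = 1.6 points |
| 10 points | 0.10 x 0.22 = 2.2 points | 0.10 x 0.32 = 3.2 points |
| 15 points | 0.15 x 0.22 = 3.3 points | 0.15 x 0.32 = 4.8 points |

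The sign follows the imbalance:

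- With 10% in monitored women, 25% in controls and r1 = 40%, the rates are 0.10 x 0.40 + 0.90 x 0.08 = 11.2% and 0.25 x 0.40 + 0.75 x 0.08 = 16.0%. That is 4.8 points in favour of monitoring.
- With 25% in monitored women and 15% in controls, they are 16.0% and 12.8%. That is 3.2 points against it.

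**3. What would that do to a test?** Assume 214 per group, all with an Edinburgh result, and a two-sided 5% test of two proportions (the plan states no significance level). The chance of a significant result in the direction of the bias is Phi[(|d| - 1.96 x SE0) / SE1], where d is the spurious difference, SE0 the pooled and SE1 the unpooled standard error. At 10% against 25%:

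- r1 = 30%: d = 3.3 points and the chance is 18.3%.
- r1 = 40%: d = 4.8 points and the chance is 30.4%.

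The nominal figure in one direction is 2.5%. At 15% against 20% the chance is 5.4% to 7.0%.

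**4. Question 42.** Section 6 says blood pressures and weights are sent through the Honeywell device, and then "These values will need to be manually uploaded into the study database program in REDCap". Questionnaire answers are not mentioned there, and Appendix I has no question 42 field. The route into the database is therefore unstated. So is the choice of response to pair with the Edinburgh score, although the question refers to a particular week.

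**The case against.** **Exploratory status.** Aims 2-5 are declared unpowered and hypothesis-generating, no imbalance in depression history has been shown, and any bias could run against monitoring. All of that stands. It makes the point a risk of unknown size and direction, and it rules out saying that 5D will credit monitoring with pre-existing differences. It does not remove the point, since the results are meant to guide later studies and the listed data offer no means of checking.

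**A general limitation.** Every comparison of these cohorts is non-randomised and unadjusted, so depression may seem singled out. That is fair, but here an obvious predictor of the outcome is absent from the data, so even an analyst who wished to adjust for it could not.

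**Feasibility.** Women come from several outpatient practices, and the documents do not show that pre-delivery history is available for all of them. This stands, and the fix must allow for missing history.

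**A stronger reading that the documents do not support.** A reader might infer that 5E cannot be computed because none of the 214 monitored women has a 1-7 score, or that it would fall back on item 130. Appendix I is headed as a chart and Peridata extraction list. It also omits the daily home blood pressures and weights, which Section 6 plainly collects and Sub-Aims 5A and 5F graph. Absence from that list is therefore not evidence that the question 42 scores are missing. No text directs 5E to item 130, which fits the depression-screening comparison in Aim 8.

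**Conclusion.** The point holds for 5D. The comparison can be computed, but an imbalance in prior depression would be inseparable from an effect of monitoring and could be neither detected nor adjusted for. Under the assumed rates (30-40% against 8%), an imbalance of 0 to 15 points produces a false difference of 0 to 4.8 points in either direction. These figures are illustrative: the documents give neither the prevalence of prior depression nor the positive-screen rates, and with equal prevalence the bias from this source is zero. The change is worth making because it is cheap, though the exploratory status of the aim limits the consequence. For 5E the finding is a minor gap in documentation; the documents do not show that the scores are unavailable.

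**What to change.** - Add one field to Appendix I for the 428 women (214 study, 214 control): depression diagnosis or antidepressant use before delivery, coded yes, no or unknown. Abstract it from records that predate delivery, by the same rule in both cohorts.
- Show the field by cohort in the baseline comparison, including the share unknown.
- In Section 7.2, state that 5D will be reported adjusted for this field beside the unadjusted rates, for example as a stratified risk difference.
- If the field cannot be abstracted, label 5D as an unadjusted descriptive comparison that does not support an effect of monitoring.
- As a documentation point, state how the 1-7 question 42 score and its date reach REDCap, and which response is paired with the Edinburgh score in 5E.

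The cost is some abstraction time in records already being reviewed. History may be incomplete in some charts, and the unknown group remains open to confounding. Adjusting for this one variable also leaves other differences between the cohorts untouched.
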